6.1.1.2.2 VESANOID - Risks

Adverse events (both non-serious and serious) associated with VESANOID will be reported to the principal investigator, the University of Colorado Data Safety Monitoring Committee (DSMC), and COMIRB. The treating medical oncologist and principal investigator will decide if VESANOID dose should be decreased or if VESANOID treatment should be discontinued.

VESANOID Side Effects

Below is a comprehensive list of reported side effects for VESANOID. Much of the reported experience is in patients being treated for APL, which may differ for patients in this trial who do not have APL.

Potential Side Effects

Virtually all patients experience some drug-related toxicity, especially headache, fever, weakness, and fatigue. These adverse effects are seldom permanent or irreversible nor do they usually require interruption of therapy. Some of the adverse events are common in patients with APL, including hemorrhage, infections, gastrointestinal hemorrhage, disseminated intravascular coagulation, pneumonia, septicemia, and cerebral hemorrhage. The following describes the adverse events, regardless of drug relationship, that were observed in patients treated with VESANOID (tretinoin).

Typical Retinoid Toxicity

The most frequently reported adverse events were similar to those described in patients taking high doses of vitamin A and included headache (86%), fever (83%), skin/mucous membrane dryness (77%), bone pain (77%), nausea/vomiting (57%), rash (54%), mucositis (26%), pruritus (20%), increased sweating (20%), visual disturbances (17%), ocular disorders (17%), alopecia (14%), skin changes (14%), changed visual acuity (6%), bone inflammation (3%), visual field defects (3%).

Body as a Whole

General disorders related to VESANOID (tretinoin) administration and/or associated with APL included malaise (66%), shivering (63%), hemorrhage (60%), infections (58%), peripheral edema (52%), pain (37%), chest discomfort (32%), edema (29%), disseminated intravascular coagulation (26%), weight increase (23%), injection site reactions (17%), anorexia (17%), weight decrease (17%), myalgia (14%), flank pain (9%), cellulitis (8%), face edema (6%), fluid imbalance (6%), pallor (6%), lymph disorders (6%), acidosis (3%), hypothermia (3%), ascites (3%).

Respiratory System Disorders

Respiratory system disorders were commonly reported in APL patients administered VESANOID (tretinoin). The majority of these events are symptoms of the RA-APL syndrome (see boxed WARNINGS). Respiratory system adverse events included upper respiratory tract disorders (63%), dyspnea (60%), respiratory insufficiency (26%), pleural effusion (20%), pneumonia (14%), rales (14%), expiratory wheezing (14%), lower respiratory tract disorders (9%), pulmonary infiltration (6%), bronchial asthma (3%), pulmonary edema (3%), larynx edema (3%), unspecified pulmonary disease (3%).

Ear Disorders

Ear disorders were consistently reported, with earache or feeling of fullness in the ears reported by 23% of the patients. Hearing loss and other unspecified auricular disorders were observed in 6% of patients, with infrequent (<1%) reports of irreversible hearing loss.

Gastrointestinal Disorders

GI disorders included GI hemorrhage (34%), abdominal pain (31%), other gastrointestinal disorders (26%), diarrhea (23%), constipation (17%), dyspepsia (14%), abdominal distention (11%), hepatosplenomegaly (9%), hepatitis (3%), ulcer (3%), and unspecified liver disorder (3%).

Cardiovascular and Heart Rate and Rhythm Disorders

Arrhythmias (23%), flushing (23%), hypotension (14%), hypertension (11%), phlebitis (11%), cardiac failure (6%) and for 3% of patients: cardiac arrest, myocardial infarction, enlarged heart, heart murmur, ischemia, stroke, myocarditis, pericarditis, pulmonary hypertension, secondary cardiomyopathy.

Central and Peripheral Nervous System Disorders and Psychiatric

Dizziness (20%), paresthesias (17%), anxiety (17%), insomnia (14%), depression (14%), confusion (11%), cerebral hemorrhage (9%), intracranial hypertension (9%), agitation (9%), hallucination (6%) and for 3% of patients: abnormal gait, agnosia, aphasia, asterixis, cerebellar edema, cerebellar disorders, convulsions, coma, CNS depression, dysarthria, encephalopathy, facial paralysis, hemiplegia, hyporeflexia, hypotaxia, no light reflex, neurologic reaction, spinal cord disorder, tremor, leg weakness, unconsciousness, dementia, forgetfulness, somnolence, slow speech.

Urinary System Disorders

Renal insufficiency (11%), dysuria (9%), acute renal failure (3%), micturition frequency (3%), renal tubular necrosis (3%), enlarged prostate (3%).

Miscellaneous Adverse Events

Isolated cases of erythema nodosum, basophilia and hyperhistaminemia, Sweet's syndrome, organomegaly, hypercalcemia, pancreatitis and myositis have been reported.

Cardiovascular

Cases of thrombosis (both venous and arterial) involving various sites (e.g., cerebrovascular accident, myocardial infarction, renal infarct) have been reported rarely.

Hematologic

Rare cases of thrombocytosis have been reported.

Skin

Genital ulceration.

Miscellaneous Adverse Events

Rare cases of vasculitis, predominantly involving the skin, have been reported.

6.1.1.2.3 Dose Modifications for VESANOID

If patients experience grade 3 or 4 toxicity that is believed to be related to the VESANOID, then the VESANOID will be held until the toxicity resolves to grade 0 or 1. In the case where the grade 3 or 4 toxicity is believed to be related to Pembrolizumab, the dose modification guidelines in table 3 will be followed. If the toxicity appears to be related to a combination of Pembrolizumab and VESANOID, the VESANOID will be held and the guidelines in table 3 will be followed. After the toxicity has resolved, the VESANOID will either be restarted at the next scheduled time at a reduced dose of 100mg/m² or will be discontinued for serious toxicities. The decision to discontinue treatment will be based on what the treating physician feels is in the subjects' best interest. If the grade 3 or 4 toxicity returns, the VESANOID will be held indefinitely.

The severity of the adverse events will be rated on a scale of Grade 1-4 and reported according to the Data and Safety Monitoring Plan using CTCAE version 4.0. Medical oncologists at the University of Colorado Hospital Cutaneous Oncology Clinic specialize in melanoma and have extensive experience treating patients with immune-based therapies that cause immune-related adverse events. The Principal Investigator will be notified of all adverse events that occur during this trial and will work with the treating oncology team to determine the likelihood of VESANOID's contribution to the adverse event.

VESANOID Related Toxicity

Significant VESANOID related toxicity is defined as any >= grade 3 nonhematologic toxicity related to VESANOID, > = grade 4 hematologic toxicity related to VESANOID or other grade VESANOID related adverse events that lead to treatment discontinuation. An exception is VESANOID related headache not optimally managed with supportive care therapies [acetaminophen, non-steroidal anti-inflammatory medication, or Imitrex (sumatriptan)] or that does not resolve within 72 hours of stopping the VESANOID. A patient's choice to stop all VESANOID, with or without a dose reduction, due to headache alone will not be considered a dose limiting toxicity.

Dose Limiting Toxicity and Study Discontinuation Criteria

The trial stopping criteria outlined in the table found in Section 6.6.5 - *Toxicity and Study Discontinuation Criteria* will be followed to avoid posing undue risk to additional patients. Twenty four (24) patients will potentially be recruited to further evaluate safety and assess preliminary efficacy.

Dose limiting toxicities are defined according to the AE profile observed during the first cycle (Cycle 1 Day 0 to Cycle 2 Day 0) of study drug administration. All AEs should be considered possibly related to the study drug unless such relationship can be definitively excluded.

Toxicity will be evaluated according to NCI CTCAE Version 4.0. A DLT will be defined as any of the following events that are considered by the investigator to be at least possibly related to treatment with Vesanoid and Pembrolizumab:

- 1. Any >= grade 3 non-hematologic toxicity related to VESANOID, > = grade 4 hematologic toxicity related to VESANOID or other grade VESANOID related adverse events that lead to treatment discontinuation. An exception is VESANOID related headache not optimally managed with supportive care therapies (acetaminophen or non-steroidal antiinflammatory medication) or that does not resolve within 72 hours of stopping the VESANOID. A patient's choice to stop all VESANOID, with or without a dose reduction, due to headache alone will not be considered a dose limiting toxicity.
- 2. Any >= grade 3 toxicity related to Pembrolizumab.

Dose Level	Number of Patients	Vesanoid	Pembrolizumab
-1	6	$100 \text{ mg/m}^2 \text{ PO on days -1, 0, and 1}$ every 3 weeks for the first 4 cycles	200 mg IV on Day 0 every 3 weeks
1 (Starting Dose)	6	150 mg/m ² PO on days -1, 0, and 1 every 3 weeks for the first 4 cycles	200 mg IV on Day 0 every 3 weeks

The dose levels will be as follows:

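### On its natural reading, the headache exception in the DLT definition exempts the worse Vesanoid headaches and counts the controlled ones, and this definition drives the 3-of-6 dose rule

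*Combined protocol and SAP*

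**What the plan says.** Section 6.1.1.2.3, under Dose Limiting Toxicity and Study Discontinuation Criteria, defines DLTs over the first cycle. Item 1 covers Vesanoid: non-hematologic toxicity of grade 3 or more, hematologic toxicity of grade 4 or more, and events of other grades that lead to stopping treatment. It then states: "An exception is VESANOID related headache not optimally managed with supportive care therapies", naming acetaminophen and NSAIDs, "or that does not resolve within 72 hours of stopping the VESANOID". The next sentence says that a patient's decision to stop Vesanoid "due to headache alone will not be considered a dose limiting toxicity". Item 2 adds "Any >= grade 3 toxicity related to Pembrolizumab", with no headache exception.

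The same section, under VESANOID Related Toxicity, repeats the exception in the same direction with a longer therapy list: "acetaminophen, non-steroidal anti-inflammatory medication, or Imitrex (sumatriptan)] or that does not resolve within 72 hours of stopping the VESANOID".

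Section 2.1 sends the reader to 6.1.1.2.3 for the DLT definition. With 0 to 2 DLTs among 6 patients the dose is kept. With 3 or more, the dose falls to 100 mg/m² after cohort 1, or the study stops after cohort 2. Table 5 in Section 6.6.5 uses the same limit. That section, however, defines toxicity as adverse events of grade 3 or higher with no headache exception, although it also speaks of evaluating DLTs.

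**The concern.** An exception to a list of DLTs is, on its face, something that is not a DLT. The events placed in the exception are the headaches that supportive care fails to control and those that outlast 72 hours off drug. What remains countable is a severe headache that responds to treatment and goes away. That is the opposite of what a safety rule would normally do, and the same wording appears twice.

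The primary objective is the MTD and RP2D (Section 3.1), and the decision rests on groups of six. Headache is also the side effect that Section 4.2.2 names when it explains the de-escalation design, from the team's earlier trial of Vesanoid with ipilimumab at the same daily dose. Staff who apply the text as written could therefore reach a different dose or stopping decision from the one the designers intended.

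**Working it through.** **Step 1: the text.** The plan states no figure for this point, so the check starts with the wording.

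| Grade 3 or higher headache, Vesanoid only | Natural reading | Likely intent |
|---|---|---|
| Uncontrolled, or lasting beyond 72 hours | not a DLT | DLT |
| Controlled and resolved within 72 hours | DLT | not a DLT |

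Section 4.2.2 describes ATRA headache as resolving once ATRA is stopped. That supports exempting the resolving kind, but the section does not state the rule. The patient-choice sentence covers only a decision by the patient. It does not settle a grade 3 or higher headache. Nor does it settle a lower-grade headache for which the physician stops the drug, a decision that Section 6.1.1.2.2 assigns elsewhere: "The treating medical oncologist and principal investigator will decide if VESANOID dose should be decreased or if VESANOID treatment should be discontinued". Vesanoid ends on day 1 of each cycle (Table 2), so the 72-hour test for a first-cycle headache falls well inside the 21-day window.

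**Step 2: effect on the decision, with no rates assumed.** In a cohort of 6, let k be the patients with another DLT. Let u be further patients with an uncontrolled or persistent grade 3 or higher headache, and c further patients with a controlled, resolving one. All these headaches are attributed to Vesanoid only.

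- Natural-reading count = k + c
- Likely-intent count = k + u
- Action is taken at a count of 3 or more

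The decisions differ when exactly one count reaches 3. If only one headache type occurs, in h patients, this means k ≤ 2 and k + h ≥ 3:

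| k | Headaches needed for opposite decisions |
|---|---|
| 2 | 1 or more |
| 1 | 2 or more |
| 0 | 3 or more |
| 3 or more | never |

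Example with k = 2 and one uncontrolled headache: the natural reading counts 2 + 0 = 2 and keeps the dose. The likely intent counts 2 + 1 = 3, so the dose is reduced (cohort 1) or the study stops (cohort 2). If that headache is controlled and resolves, the counts are 3 and 2 and the decisions swap. With one headache of each type the counts are equal and nothing changes.

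**Step 3: illustration with assumed rates.** Let b be the rate of other DLTs, h now the rate of grade 3 or higher Vesanoid-only headache (independent of b), and s the share of those headaches that the reading counts. Then p = 1 − (1 − b)(1 − h·s), and the rule fires with probability P(X ≥ 3), X ~ Binomial(6, p). I take b = 0.24, from the 14% plus 10% in Section 6.6.5 read as percentage points. This is only a stand-in, because those are overall toxicity rates. The values of h and the 25% uncontrolled share are assumptions.

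- h = 0.20, natural reading (s = 0.75): p = 1 − 0.76 × 0.85 = 0.354, P = 0.361
- h = 0.20, likely intent (s = 0.25): p = 1 − 0.76 × 0.95 = 0.278, P = 0.216
- h = 0.10: P = 0.250 and 0.184
- h = 0.05: P = 0.200 and 0.169

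If 75% are uncontrolled instead, each pair swaps. At 50% there is no difference. With b = 0.14 and 25% uncontrolled, the pairs run from 0.068 and 0.048 (h = 0.05) to 0.201 and 0.079 (h = 0.20). Apart from the 50% case, the gap is therefore about 0.02 to 0.15, in either direction.

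**The case against.** The sentence does not say what it is an exception to. It could be read as taking headache out of the general grade thresholds and giving it its own test, under which unmanaged or persistent headache is a DLT. That reading reaches the presumed intent, but the sentence does not say it. The first limb alone could also mean that a headache not yet given proper supportive care is not a fair DLT. The 72-hour limb allows no such reading.

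The stronger objection concerns consequence, and much of it stands. Section 6.1.1.2.3 presumes that adverse events are possibly related to study drug unless this is definitively excluded. Section 6.1.1.2 warns that the two toxicity profiles may overlap. If the presumption extends to pembrolizumab, many grade 3 or higher headaches would count under item 2 on either reading. Headaches attributed to Vesanoid alone may therefore be few. For a Vesanoid-related grade 3 or 4 event the individual patient is still protected: "then the VESANOID will be held until the toxicity resolves to grade 0 or 1". The sponsor-investigator's dose review uses the available adverse event and laboratory data, and the DSMC has oversight. These safeguards narrow the problem but do not tell anyone which headaches to count.

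A reader might infer that the exception hides severe headache and so biases the RP2D upward. The documents do not support that. If headaches mostly resolve on stopping, as Section 4.2.2 describes, the natural reading would mainly over-count DLTs. A reader might also take the 86% headache figure in Section 6.1.1.2.2 as the rate at stake. That figure covers reported headache without restriction by grade, in APL patients and regardless of drug relationship. It is not a DLT rate.

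**Conclusion.** Wrong as written. On its natural reading the rule runs opposite to its likely purpose, appears twice, is corrected nowhere, and feeds the decision that serves the primary objective. One Vesanoid-only headache is enough to reverse a cohort decision when two other patients have DLTs.

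The conclusion rests on the natural meaning of the sentence and on the link from Section 2.1. The intent is inferred, not documented. Size and direction are unknown, because no grade 3 or higher headache rate is given and Section 4.2.2 says that the earlier report gave neither frequency nor severity. The mismatch with Section 6.6.5 and the differing therapy lists are secondary.

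**What to change.** Have the investigators confirm the intent and the therapy list. Then replace only the exception sentence in the DLT definition with, for example:

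> Exception: a Vesanoid-related headache that meets the criteria above is not a DLT if supportive care (acetaminophen, an NSAID or sumatriptan) controls it and it resolves within 72 hours of stopping Vesanoid. If it is not controlled, or has not resolved by 72 hours, it is a DLT.

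Keep the patient-choice sentence. Add no grade limit: that would newly exempt a lower-grade headache for which the physician stops Vesanoid, which item 1 otherwise counts. Make the matching change, with the same therapy list, under VESANOID Related Toxicity.

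In Section 6.6.5, state that Table 5 counts DLTs as defined in 6.1.1.2.3, and replace the sentence after the table with:

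> If 3 or more of the 6 patients in cohort 1 have a DLT, the next 6 enrolled patients (cohort 2) will receive Vesanoid 100 mg/m².

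Putting DLTs into the existing 33% sentence would not be enough. Two of six is 33.3%, which exceeds 33%, so it would contradict the rule in Section 2.1 that keeps the dose at 0 to 2.

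The cost is a short protocol amendment. Visits, sample size and the 3-of-6 limit do not change. The counted DLT rate may move in either direction.

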6.1.2 Timing of Dose Administration

Trial treatment with Pembrolizumab should be administered on Day 0 of each cycle after all procedures/assessments have been completed as detailed on the *Trial Schedule of Events Chart (Section 7.1)*. All trial treatments will be administered on an outpatient basis. VESANOID will be administered on day -1, 0 and 1 with each of the first four cycles of Pembrolizumab. VESANOID will be administered twice a day (75mg/m² each dose for a total dose of 150mg/m²).

Pembrolizumab 200 mg will be administered as a 30-minute IV infusion every 3 weeks. Given the variability of infusion pumps from site to site, a window of -10 minutes and +10 minutes is permitted (i.e., infusion time is 30 minutes: -10 min/+10 min).

The Pharmacy Manual and investigational brochure contains specific instructions for the preparation of the pembrolizumab infusion fluid and administration of infusion solution.

6.1.3 Trial Blinding/Masking

This is an open-label trial; therefore, the Sponsor-Investigator, study personnel, and subject will know the treatment administered.

6.2 Concomitant Medications/Vaccinations (allowed & prohibited)

Medications or vaccinations specifically prohibited in the exclusion criteria are not allowed during the ongoing trial. If there is a clinical indication for one of these or other medications or vaccinations specifically prohibited during the trial, discontinuation from trial therapy or vaccination may be required. The final decision on any supportive therapy or vaccination rests with the Sponsor-Investigator and/or the subject's primary physician.

6.2.1 Acceptable Concomitant Medications

All treatments that the investigator considers necessary for a subject's welfare may be administered at the discretion of the investigator in keeping with the community standards of medical care. All concomitant medication will be recorded on the case report form (CRF) including all prescription, over-the-counter (OTC), herbal supplements, and IV medications and fluids. If changes occur during the trial period, documentation of drug dosage, frequency, route, and date may also be included on the CRF.

All concomitant medications received within 28 days before the first dose of trial treatment and 30 days after the last dose of trial treatment should be recorded. Concomitant medications administered after 30 days after the last dose of trial treatment should be recorded for SAEs and ECIs as defined in Section 7.5 – *Events of Clinical Interest (ECI)*.

6.2.2 Prohibited Concomitant Medications

Subjects are prohibited from receiving the following therapies during the Screening and Treatment Phase (including retreatment for post-complete response relapse) of this trial:

- Antineoplastic systemic chemotherapy or biological therapy
- Immunotherapy not specified in this protocol
- Chemotherapy not specified in this protocol
- Radiation therapy
 - Note: Radiation therapy to a symptomatic solitary lesion or to the brain may be allowed at the investigator's discretion.
- Live vaccines within 30 days prior to the first dose of trial treatment and while participating in the trial. Examples of live vaccines include, but are not limited to, the following: measles, mumps, rubella, varicella/zoster, yellow fever, rabies, BCG, and typhoid vaccine.
- Systemic glucocorticoids for any purpose other than to modulate symptoms from an event of clinical interest of suspected immunologic etiology. The use of physiologic doses of corticosteroids may be approved after consultation with the Sponsor-Investigator.

Subjects who, in the assessment by the investigator, require the use of any of the aforementioned treatments for clinical management should be removed from the trial. Subjects may receive other medications that the investigator deems to be medically necessary.

The Exclusion Criteria describes other medications that are prohibited in this trial.

There are no prohibited therapies during the Post-Treatment Follow-up Phase.

6.3 Rescue Medications & Supportive Care

6.3.1 Supportive Care Guidelines

Subjects should receive appropriate supportive care measures as deemed necessary by the treating investigator. Suggested supportive care measures for the management of adverse events with potential immunologic etiology are outlined below. Where appropriate, these guidelines include the use of oral or intravenous treatment with corticosteroids as well as additional anti-inflammatory agents if symptoms do not improve with administration of corticosteroids. Note that several courses of steroid tapering may be necessary as symptoms may worsen when the steroid dose is decreased. For each disorder, attempts should be made to rule out other causes such as metastatic disease or bacterial or viral infection, which might require additional supportive care. The treatment guidelines are intended to be applied when the investigator determines the events to be related to pembrolizumab.

Note: if after the evaluation the event is determined not to be related, the investigator does not need to follow the treatment guidance (as outlined below). Refer to Section 6.1.1.2 - *Dose Modification (Escalation/Titration/Other)*.

6.4 Known Potential Benefits of the Trial

The risks to subjects are reasonable in relation to the anticipated benefits to subjects and/or society, and in relation to the importance of the knowledge that may reasonably be expected to result, thereby falling in favor of performing the study:

- To Subject: The potential benefit to the study subject is decreased immunosuppressive action of MDSC's and enhanced immunologic responses.
- To Society: The potential benefit to society is generalizable knowledge regarding utilization of combinational immunotherapies.
- Justify the importance of the knowledge gained: The potential knowledge to be gained includes a better understanding of mechanisms surrounding ongoing tumor induced immunosuppression. Information from this study may be used to further refine immunologic targets such as MDSC's.

